Feeding in neonates involves a sequence of sucking, swallowing, and breathing that requires coordination of the face, head, and neck muscles with the myelinated vagal regulation of the bronchi and the heart (11). In preterm neonates, the muscles needed to feed are underdeveloped, resulting in the need for OT rehabilitation to 'learn' feeding patterns. Preterm neonates' inability to feed effectively is the primary reason for prolonged hospital stays (12). In neonates with HIE, development of cortex and basal ganglia is interrupted, and depending on the severity, normal developmental plasticity is hindered, further contributing to their inability to feed (13). Both types of feeding difficulties involve complex motor learning, which requires integration of sensory and motor pathways. Treating oromotor difficulties during the learned task of feeding with noninvasive brain stimulation that promotes plasticity, poses a highly novel application of taVNS. Our major premise is that in babies at high risk for motor problems, simultaneously delivered brain stimulation via taVNS will boost motor cortical plasticity involved in a learned feeding task, leading to better feeding.

This protocol has 2 specific aims that will be investigated:

Specific Aim 1: Improved Motor Learning - We aim to investigate whether pairing taVNS with rehabilitation training of feeding behavior in preterm and HIE neonates will enhance and accelerate the learning of effective feeding behavior in a dose responsive manner. We call this treatment "taVNS-paired feeding." The primary outcome measures of taVNS-paired feeding will be daily oral milk feeding volume changes from before to during treatment, and number of infants reaching full oral feeds

between once and twice daily taVNS-paired feeding, duration to full feeds, as well as general motor functional impairment as measured by [name] Test of Early infant motor Performance (STEP). Our hypothesis is that taVNS-paired feeding for preterm neonates is feasible, safe and effective at reducing length of stay solely for feeding reasons, compared to historical controls. As part of our safety investigations with separate funding, we may perform taVNS during a clinical modified barium swallow study with pediatric speech language pathologists performing the study and compare 10 swallows with stimulation on and off to determine if taVNS affects swallowing parameters.

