Specific Aim 2: Brain Changes - We aim to determine if white matter fiber tracts show improved integrity as measured by diffusion imaging (DKI) before, after a 2-week treatment taVNS-paired feeding course, and whether treatment improves neuronal energetics in the basal ganglia as measured by magnetic resonance spectroscopy (MRS). Unsedated MRS and DKI imaging will last approximately 40 minutes, and will be done before and after the two-week taVNS-paired rehab treatment session. The changes in white matter tract diffusion parameters and N-acetylaspartate (NAA) and glutathione (GSH) concentration in the basal ganglia and thalamus will be compared with published changes of these parameters over gestational age in preterm infants (14, 15) and with our own MRS data in preterm and HIE infants who did not receive taVNS.

We will perform DKI to determine the effects of taVNS on plasticity, and to identify areas of the brain involved in afferent vagal activation. We propose utilizing the concurrent taVNS/fMRI method developed by [name] at MUSC to determine whether taVNS activates the CNS and afferent vagal network in a subset of preterm and term infants in the study.

B. BACKGROUND AND SIGNIFICANCE

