Up to 40 preterm/HIE neonates will be enrolled in this prospective, open-label safety and feasibility trial, with a dose response. The experimental paradigm consists of 2 to 3 weeks of once or twice daily taVNS-paired feeding.

Our control group was investigated by Drs. [name] and [name] at MUSC, who have researched all infants failing feeding and getting Gastrostomy tubes in our nurseries over the past 5 years. We can compare our data to this historical group at our own institution.

All consented participants will receive the active stimulation condition.

taVNS Stimulation (in Detail)

After obtaining consent and describing this procedure to the parents and all members of the baby's care team, we will first, with a 500 μ s, 25Hz pulse, gradually increase the intensity of the TENS unit until the baby can first feel something in their ear. We will use the facial expression change and fidgety movements to determine when the infants feel the stimulation. This intensity will be recorded as the perceptual sensory threshold. The stimulation intensity we will use for this study on taVNS-paired feeding is a small decrement from the perceptual sensory threshold for each infant (-0.1mA), a point at which they should not react to the stimulation. We will retest the sensory threshold before every session.

Determination of Perceptual Threshold

1. Electrode clip will be placed on the left tragus in an enrolled infant at rest. Starting at 0.2mA at 25Hz, we will deliver 5 seconds of pulses, and increase by 0.1mA until the perceptual threshold is achieved by observation of the infant's facial expression, fidgety movements, or NIPPS score. This will be termed the perceptual threshold.
2. We will then deliver this level of microcurrent while the infant is feeding on the first day to determine if the perceptual threshold changes with feeding. Current will then be held constant while pulse width and frequency will be set at 500us and 25Hz, respectively.

3. Finally, we will decrease the microcurrent by 0.1mA *below the perceptual threshold* and administer this taVNS treatment during the feeding and deliver this only while the infant is actively sucking from the bottle.
4. The total duration of this 'on-and-off' taVNS stimulation treatment will continue for 30 minutes or the duration of the feed.
5. We may manually trigger the taVNS stimulation or place a gel EMG electrode over the temporomandibular joint area to trigger the taVNS impulse.

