For safety we will compare HR changes from baseline to during taVNS within subjects. We will compare treatment before and after the taVNS-paired feeding treatment for the rate of feeding volume increase, and days to full po feeds. We will use repeated measures ANOVA to analyze repeated measures such as HR over 5 minutes and mean daily feeding volumes in 7-10 day epochs. We will analyze the number of infants who reach full feeds vs requiring G-tube during taVNS-paired feeding, between once and twice daily stimulation by Chi-squared. We will assess differences in kurtosis parameters from pre-to post taVNS scans by paired t-test, and between those that reach full oral feeds vs those that require a Gtube by unpaired t-test.

Estimated Difficulties, Limitations and Time Frames

Estimated Difficulties. Many of the initial parameters for taVNS in humans, such as frequency and pulse width, were accomplished in trials at MUSC by [name] et al. that were approved by the IRB. In one sense, we will be shrinking many of the components into miniature form to deliver stimulation to neonates and infants. In spite of the clear differences in size and skin between the neonatal and adult ear, the custom electrodes have been fitted to several different weights of infants (2.5-4.0 kg).

Limitations. We will not be delivering a SHAM stimulation paradigm (electrodes and Digitizer with appearance of taVNs treatment without actual current). Our goal is to determine safety and feasibility of active treatment with a dose response in order to investigate whether this should be administered in a larger randomized control trial. In this respect, the comparison we lose in not having a SHAM stimulation is offset by the validation we will receive in the safety and feasibility of active treatment. We will compare our overall results with characteristics of infants who required a Gtube from [name] and [name]'s publications.

Estimated Time Frames. The duration of the study will likely be ~4 years, with 2 years of active enrollment and 18 months of follow-up.

E. PROTECTION OF HUMAN SUBJECTS

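### The kurtosis comparison between full-feed and G-tube infants is an unadjusted t-test that does not say whether post-treatment values or pre-to-post changes are tested

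*Combined protocol and SAP*

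**What the plan says.** Section D, Data Analysis, gives the kurtosis analysis in one sentence with two parts. The first is within infant: "We will assess differences in kurtosis parameters from pre-to post taVNS scans by paired t-test". The second is between outcome groups: "between those that reach full oral feeds vs those that require a Gtube by unpaired t-test". No baseline term, other covariate or definition of the analysed variable is given for the second part.

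Three other places bear on it:

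- Section A, Specific Aim 2, states that the imaging "will be done before and after the two-week taVNS-paired rehab treatment session", so a pre-treatment value is collected by design.
- Section D, Study Design, states: "All consented participants will receive the active stimulation condition". Full-feed and G-tube infants are therefore outcome groups within one treated cohort.
- Section A, shortly before the aims are listed, states: "In neonates with HIE, development of cortex and basal ganglia is interrupted, and depending on the severity, normal developmental plasticity is hindered". The same sentence ties this to the inability to feed.

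**The concern.** Brain condition at entry plausibly influences both the kurtosis measurements and the group an infant ends up in. Section A supplies that path itself, and Section D, Participants, admits preterm infants alongside term infants with HIE or other serious illness. A baseline difference between the outcome groups is therefore to be expected.

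An unpaired t-test on post-treatment scans is a valid test of whether the groups differ at that scan. It cannot tell a difference that was there beforehand from one that developed during the course. The pre-treatment scan holds the information needed to separate the two, and the plan does not say whether this test uses it. Left open, the choice could be made after the data are seen.

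Aim 2 concerns change: "We aim to determine if white matter fiber tracts show improved integrity as measured by diffusion imaging (DKI) before, after a 2-week treatment". A between-group difference that predates stimulation does not bear on that question, yet could easily be placed beside it in a report.

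**Working it through.** The plan gives no significance level, power, SD or effect size for this comparison, so there is no figure to reproduce. The calculation below is illustrative.

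**From the documents.** Sample size: "Up to 40 preterm/HIE neonates will be enrolled in this prospective, open-label safety and feasibility trial, with a dose response". The sizes of the two outcome groups are not given.

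**Assumed.** All 40 infants have both scans; split 20/20, with 24/16 as a check; two-sided 5% test; equal SD of 1 at both scans; a baseline gap between the groups that stays constant, so there is no differential change; pre-post correlation r of 0.5, 0.7 or 0.9.

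**Post-treatment values only.** The noncentrality parameter is gap / √(1/n₁ + 1/n₂). For 0.5 SD and 20/20 it is 0.5 / √(0.05 + 0.05) = 1.58 on 38 degrees of freedom, and the exact noncentral t gives 33.8% significant. Gaps of 0.3, 0.8 and 1.0 SD give 15.2%, 69.3% and 86.9%. With 24/16, the 0.5 and 0.8 SD gaps give 32.7% and 67.6%.

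**Change, and baseline-adjusted model.** These come from 10,000 simulated trials per setting (20/20; proportion significant with no differential change):

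| Gap (SD) | Post only | Change | Adjusted, r = 0.5 | r = 0.7 | r = 0.9 |
|---|---|---|---|---|---|
| 0.3 | 15% | 5% | 8% | 7% | 5% |
| 0.5 | 34% | 5% | 14% | 9% | 6% |
| 0.8 | 69% | 5% | 26% | 17% | 8% |
| 1.0 | 87% | 5% | 35% | 21% | 10% |

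A stable gap cancels in the change score. Baseline adjustment leaves gap × (1 − r). For a 0.5 SD gap that is 0.5 × 0.5 = 0.25 SD at r = 0.5, 0.5 × 0.3 = 0.15 SD at r = 0.7 and 0.5 × 0.1 = 0.05 SD at r = 0.9.

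**The reverse case.** Suppose instead that both groups regress towards a common mean. At r = 0.7 a 0.5 SD gap becomes 0.7 × 0.5 = 0.35 SD at the second scan. The change score then shows 0.35 − 0.50 = −0.15 SD, while the adjusted estimate is 0.35 − 0.7 × 0.5 = 0. Which analysis is unbiased depends on how the gap would have evolved, and the two scans cannot settle that.

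**Precision.** Relative residual variance is 1 for post only, 2(1 − r) for change and 1 − r² for adjustment. At r = 0.5 these are 1, 1.00 and 0.75; at r = 0.7 they are 1, 0.60 and 0.51.

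**The case against.** The strongest reply is grammatical. The object of the sentence is differences from pre to post, and this can carry over to the second part. The unpaired test would then compare changes, the pre-treatment scan would be used, and a stable gap would cancel. This stands as a possible reading. A reader might infer that the plan discards the pre-treatment scan; the text does not establish that. It leaves the variable undefined.

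A second reply is that the harm is inferred. A reader might infer that the sponsor will present this contrast as an effect of taVNS. The documents do not say so. The question in Aim 2 is served by the paired test, with an external comparator, since imaging changes "will be compared with published changes of these parameters over gestational age in preterm infants" and with the site's own spectroscopy data from untreated infants. Section B calls imaging a secondary purpose, and Section D, Limitations, openly states that there is no sham arm. This stands too, although nothing in Data Analysis says the contrast is only associative.

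Third, replacing the t-test by baseline adjustment alone is not clearly better. If the sponsor means change scores, the switch could introduce bias that was not there. This is correct, and it is why both analyses are recommended.

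Finally, a reader might infer a large family-wise error across tracts and parameters. The documents use both words in the plural but give no counts, so any such figure is an assumption. Correlation among parameters would also pull it below what independent tests would give.

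**Conclusion.** The point holds in limited form. The comparison has no baseline, age or interval term, and its analysed variable is not stated. The reading matters: with a stable 0.5 SD gap and 20 infants per group, about 34% of trials would be significant under post-only testing and about 5% under change scores, with no differential change in either case. The gap, its stability, the split and the assumption that all 40 infants have both scans are not in the documents, so these percentages show scale and are not predictions. Fewer scanned infants would lower the post-only rate for a given gap.

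No version of this test isolates an effect of taVNS, with or without adjustment, because both groups are treated and are defined by what happens afterwards. It can show only an association with feeding outcome. The matter goes beyond missing detail, because scans already planned allow a better analysis at almost no cost.

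**What to change.** In Section D, Data Analysis:

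1. State that post-treatment kurtosis will not be tested alone, and name pre-to-post change as the analysed variable.
2. Report beside it a linear model of the post-treatment value on outcome group, pre-treatment value, post-menstrual age at scan and scan interval. Add diagnosis (preterm, or HIE/other) if numbers allow. Interval belongs in the model because Study Design allows a course of 2 to 3 weeks, while Aim 2 describes scans around two weeks.
3. Say that change scores are exposed to regression to the mean and that adjustment leaves part of a stable gap, so agreement between the two carries more weight than either alone.
4. Tabulate pre-treatment kurtosis by outcome group.
5. Label the result an exploratory association with feeding outcome in treated infants.
6. List the tracts and parameters. False discovery rate control is optional for an exploratory analysis.

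No new data are needed: Section E has birth history taken from the medical record and MRI files stored with the date of scan. The cost is wording and a few degrees of freedom among at most 40 infants.

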1. RISKS TO THE SUBJECTS

The human subjects involved in this research will be preterm neonates or infants with critical illnesses that preclude oral feeding, such as HIE. Inclusion criteria involves 2 main groups. The first is comprised of typical pre-term, high risk neonates who are in the convalescent near and post-term period and learning to po feed. The second is comprised of neonates that present after severe medical illnesses or brain injury. In both cases, the infants can only be enrolled if they are stable, not making progress with OT training, and are in discussion for Gtube placement. Participants will be excluded if they have major unrepairs congenital abnormalities that limit volume of feeds, cardiomyopathy, significant autonomic instability, such as repetitive, unresolved bradycardia or apnea, or use a continuous positive airway pressure (CPAP) device or other form of high respiratory support preventing them from breathing without assistance.

Targeted/Planned Enrollment Table

Total Planned Enrollment: 40 babies (active)

TARGETED/PLANNED ENROLLMENT: Number of Subjects receiving active taVNS			
Ethnic Category	Sex/Gender		
	Females	Males	Total
Hispanic or Latino	4	5	9
Not Hispanic or Latino	15	16	31
Ethnic Category: Total of All Subjects*			

Racial Categories			
American Indian/Alaska Native			
Asian			
Native Hawaiian or Other Pacific Islander			
Black or African American	8	7	15
White	12	13	25
Racial Categories: Total of All Subjects*	20	20	40

*The “Ethnic Category: Total of All Subjects” must be equal to the “Racial Categories: Total of All Subjects”.

Volunteers of all ethnicities and racial categories will be accepted into this study protocol. No preference will be given based on race, gender or ethnicity. No vulnerable populations or special classes of subjects will be considered for participation.

b. Sources of Materials

Participants will be screened for eligibility in person by the PI ([name]). All participants enrolling in the study will be given an alphanumerical code that will be used to identify them. This code will be used to link participants to any identifying demographic information that is collected. Only the principal investigator and appropriate study staff will have access to the documents linking identifying information with alphanumerical codes. Infant data on medical conditions, significant clinical events including birth history, and postnatal course, as well as medications, and surgeries will be collected from EPIC.

c. Potential Risks

taVNS has been conducted in individuals under the age of 18. Moreover, TENS has been used in several studies in neonates and young infants as detailed below. A summary of potential risks in infants include the risk of skin irritation, discomfort, slightly decreased heart rate, and loss of confidentiality. The potential risks have been clearly outlined in the informed consent document. There are no alternative treatments, except the standard infant feeding with OT, speech or nurses.

Potential Risks of taVNS

taVNS is transcutaneous electrical nerve stimulation (TENS) of the auricular branch of the vagus nerve (ABVN) that innervates the ear. Although this novel therapeutic modality is still in the development and optimization process, risks are a combination of those to be expected by both the peripheral TENS and implantable cervical VNS.

TENS devices are FDA approved for pain relief and are available over the counter. The main risks associated with TENS are electrical hazards that may result in user discomfort or injury. The unit used

in these studies (Digitimer DS7AH) is a 510(k) cleared electrical stimulator that meets the rigorous electrical standards of the FDA. The Soterix[©] taVNS unit has been customized for our infants with a maximum current delivery of 2 mA and automatic shut-off after 120 seconds (See uploaded documents and letter from Soterix). The customized Soterix unit will be used in our BabyStrong device which has received Breakthrough Device designation from the FDA 12/8/2020. Skin irritation, redness, or inflammation may occur under the stimulating electrodes if TENS current is delivered for a prolonged period of time.

Two studies have used TENS on neonates to try to prevent or mitigate painful procedures (39-40). The TENS was administered at acupuncture sites with increasing current from 1-3.5 mA, and Hz from 2-10 in 30 healthy infants <3 days old. (39) In a subsequent study, this investigative team randomized 162 term neonates to TENS (3.5mA, 10Hz) or usual care to prevent pain from lancet heelsticks for blood sampling (40). These TENS parameters were safe and did not cause discomfort in the neonates.

TENS has also been used with passive stretching in neonatal torticollis at 8Hz, 0.2mA for 30 minutes continuously (41) and in brachial plexus nerve injuries starting at 6 weeks of age to improve motor function of the hand, in conjunction with constraint induced movement therapy (42). Neither study reported adverse effects of electrical stimulation. TENS has also been used in peroneal and sacral nerve stimulation for dysfunctional voiding and stooling (44-45). Finally, the routine sweat test employed in newborns and infants to confirm the diagnosis of cystic fibrosis uses transcutaneous electrical stimulation to deliver pilocarpine via iontophoresis (43). From the product brochure of the Nanoduct[™] Neonatal Sweat Analysis System (Discovery Diagnostics, Canada), the nominal current is 0.5 (\pm 0.02) mA up to 5 mA for 2.5 minutes (\pm 0.2 Sec.).

Implantable cervical VNS is FDA approved for the treatment of treatment resistant depression and intractable epilepsy in children as young as 8 months (47-49). Cervical VNS has risks associated with the procedure of implanting the nerve, and the surgery. None of those apply here. VNS does have some minimal risks that are due to the actual stimulation of the nerve within the neck such as skin irritation. tVNS also has associated risks that may arise from the direct brain effects stimulating the vagus nerve. These theoretical risks associated with neuromodulation of the parasympathetic nervous system would also be applicable in the administration of noninvasive tVNS. They are the following: reduction of heart rate, blood pressure, and vasovagal syncope.

There have been dozens of studies in which tVNS has been used on humans, none of them reporting adverse events. A simple PubMed search for “transcutaneous vagus nerve stimulation” shows 24 peer-reviewed articles, 15 of which have been published within the past 3 years. See below table for 10 most recent publications on PubMed involving tVNS on the auricular branch of the vagus in humans:

Author, Year	Aim (subject number)	Side effects/Risks/AEs
Aihua et al, 2014	Epilepsy (n= 60)	Dizziness, drowsiness
Capone et al, 2014	Cortical excitability (n=10)	No modification of instantaneous HR, systolic BP, diastolic BP, and mean BP
Kreuzer et al, 2014	Tinnitus (n=50)	Twitching and pressure at electrode site
Rong et al, 2014	Epilepsy (n=144)	None reported

Kraus et al, 2013	tVNS/fMRI (n=16)	A bright, prickling sensation, twinge or stabbing pain
Rong et al, 2012	Depression (n=120)	None Reported – trial still under progress
Kreuzer et al, 2012	Safety Study (n=24)	In those subjects with no known pre-existing cardiac pathology, preliminary data do not indicate arrhythmic effects of tVNS
Busch et al, 2013	Pain (n=48)	No relevant alterations of cardiac or breathing activity or clinical relevant side effects were observed during t-VNS
Stefan et al, 2012	Epilepsy (n=10)	Hoarseness, headache, or constipation
Polak et al, 2009	Far field potentials (n=20)	Slight pain at electrode site

An extremely thorough review of all tVNS literature has been performed and no harm or adverse events have been observed and any side effects were resolved by decreasing current intensity. There is also currently a commercial tVNS device available for purchase on the European market (Cerbomed - Nemos device; www.cerbomed.com) that is marketed as a take-home treatment for epilepsy.

Not only does the current literature show a lack of harm done by tVNS, implantable cervical VNS also has a good safety record. According to Cyberonics, the company that supplies the cervical VNS implantable devices, there has been over 100,000 implanted patients being monitored by over 3,000 providing physicians. Most side effects range from alteration of voice, coughing, pharyngitis, hoarseness, headache, and nausea. Cardiac evaluations have been made on hundreds of VNS patients with no changes in cardiac function (Handforth et al, 1998; Sackeim et al, 2001b; Morris and Mueller, 1999) with long-term safety confirmed in recent large sample retrospective studies (Menascu et al, 2013; Ryvlin et al, 2014; Choi et al, 2013).

Bradycardia: [name] own safety studies in adults and this pilot study in infants designate a small, measurable change in heart rate which is not clinically significant (-3 and +6 bpm). Given the minimal risk of both of these already FDA approved methods, we intend to show that taVNS will continue to be a very safe procedure in neonates.

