[name], Ph.D, obtained his doctorate under [name], and has extensive experience and background in clinical TMS and taVNS, especially in the development of novel protocols for neurological disorders. His thesis work involves systematic elucidation of the dose response of taVNS on heart rate, use of heart rate as a biomarker of taVNS effect, and the use of taVNS with fMRI in determining pathways and regions affected by taVNS in adults. He determined that the 'on' pulse heart rate change was a mean of -3 beats per minute (bpm) while the 'off' pulse heart rate change was +6 bpm. Although these are statistically significant and measurable changes, they are physiologically insignificant. Nevertheless, this will be an important biomarker for infants, but is not expected to result in safety concerns. [name] careful and thorough studies lay the safety and efficacy groundwork for the current proposal.

D. RESEARCH DESIGN AND METHODS (including data analysis)

Due to the novelty of these studies, [name] will be present for each taVNS-paired feeding session conducted in the first participants, and as needed thereafter. [name] and or [name] will monitor taVNS effects. If any adverse events are noticed which are not described in the consent or are serious, we will inform the IRB before continuing with the next enrolled subject. Importantly, all of these methods have been done before, and published by our and other groups in adults, and we believe these extra precautions will assure the safety and well-being of any participants enrolled.

taVNS-paired feeding to enhance feeding behavior in neonates

Screening

Prospective participants will be identified by the PI ([name]) at the MUSC neonatal intensive care units (Level II and III), and checked for potential inclusion (please see the uploaded taVNS screening form). [name], and other clinical OTs based in the nursery may also mention the study to parents and refer them to [name] if they are interested in participating.

Participants

Inclusion criteria:

Infants must be clinically stable, on minimal respiratory support (nasal cannula, or room air), in discussions about Gtube placement for poor po feeding and are currently greater than or equal to 39 weeks post-menstrual age and

- 1) If born premature have been working on oral feeding for 30days;
or

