- 2) If term Infant with significant medical issues that have precluded oral feeding, such as hypoxic ischemic encephalopathy (HIE), have been working on oral feeding for 14days.

Exclusion criteria:

- 1) Unstable infants or those requiring respiratory support involving positive pressure.
- 2) Major unrepaired congenital anomalies
- 3) Anomalies/conditions that limit feeding volumes
- 4) Cardiomyopathy
- 5) Repeated episodes of autonomic instability (apnea or bradycardia) which are not self-resolving *

*Preterm infants commonly have short periods of shallow or absent breathing or lower heart rate termed apnea and bradycardia, respectively, and most are being treated for these physiologic manifestations of prematurity with caffeine, an effective central stimulant. Infants are on cardiorespiratory monitors through the nursery stay to capture events, many of which are self-resolving. Infants who require repeated episodes of tactile stimulation to come out of these events are defined as *unstable*.

Neonates who are beginning oral feeds after medical treatment for critical illnesses, such as HIE brain injury, will be included as these neonates represent a population in which taVNS-paired feeding could present the largest success in overcoming impaired brain development. Congenital syndromes may be included if the infants do not have major, unrepaired anomalies or anomalies that limit feeding volumes.

Written informed consent will be obtained from the mother if available and if she has custody or decision making authority for the participant, otherwise a parent or legal guardian, prior to participation in the experimental paradigm. Department of Social services may have custody of infant but require the parent or foster parent to consent for all medical procedures.

Electronic Consent will be used for situations when the parent (or Legally Authorized Representative) is at another hospital and cannot travel to MUSC to provide consent in person. We will use the approved REDcap system to obtain consent. [name] or other approved study personnel will go over the entire consent document on the phone with the parent to ensure comprehension and to confirm identity. Parent will be given a copy of the completed, signed consent form in person or by email or fax.

Study Design

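### The rate comparison leaves 'before' undefined; if those days overlap the stall that qualified the infant, regression to the mean favours taVNS

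*Combined protocol and SAP*

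**What the plan says.** **Selection.** Section E.1 (Risks to the Subjects) states, for both the preterm and the HIE or severe-illness group, that "the infants can only be enrolled if they are stable, not making progress with OT training, and are in discussion for Gtube placement". The inclusion criteria in section D ask for infants "in discussions about Gtube placement for poor po feeding" and set a minimum period of oral feeding: "If born premature have been working on oral feeding for 30days" for preterm infants, and for term infants that they "have been working on oral feeding for 14days". No number or time window defines lack of progress.

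**Outcome.** Specific Aim 1 places "daily oral milk feeding volume changes from before to during treatment" among the primary outcome measures. Data Analysis says: "We will compare treatment before and after the taVNS-paired feeding treatment for the rate of feeding volume increase". It also plans repeated measures ANOVA on "mean daily feeding volumes in 7-10 day epochs". Neither section defines the 'before' days, and no run-in or separate baseline is described.

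**Control.** Study Design states: "All consented participants will receive the active stimulation condition". Limitations confirms that there is no sham. The only external comparator is a historical group of infants from the same nurseries who failed oral feeding and received a G-tube.

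**The concern.** Progress is change over time. An entry rule that requires no progress therefore selects infants on a low recent rate of gain, and the planned analysis uses the pre-treatment rate as its comparator. Any temporary part of the stall, such as a passing illness, tiredness or day-to-day noise, is in the 'before' rate because of the selection and is not expected to persist. The later rate then rises on average even if stimulation does nothing.

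This differs from natural maturation, which pushes in the same direction. Where the windows overlap, modelling the pre-treatment slope does not remove the problem, because that slope is the selected quantity. The historical group does not help either: it was chosen on a bad eventual outcome, so it cannot show how far an enrolled but untreated infant would rebound.

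At stake is the reading of the feeding result. Limitations says the study is meant to inform whether a larger randomised trial should follow.

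**Working it through.** The plan gives no alpha, SD, correlation, effect size or power calculation for feeding, so there is no figure to reproduce. The inputs from the documents are up to 40 infants (Study Design), 30 or 14 days of oral feeding at entry (inclusion criteria) and 7-10 day epochs (Data Analysis). Everything else below is assumed.

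**1. Windows coincide.** Let q be the share of infants with the lowest 'before' rates who are enrolled, and r the before/after correlation without treatment. With no treatment effect and no trend, the expected gain in SDs of the rate is (1 − r) × φ(z_q) / q.

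- q = 0.25: φ(−0.6745) / 0.25 = 0.3178 / 0.25 = 1.271
- q = 0.50: φ(0) / 0.50 = 0.3989 / 0.50 = 0.798

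The plan names no test for the rate comparison. A two-sided paired t-test at 0.05 with n = 40 is assumed here, so the nominal favourable false-positive rate is 2.5%. The percentages are simulated, with Monte Carlo error of about one percentage point.

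| r | Gain, lowest quarter | False positive | Gain, lowest half | False positive |
|---|---|---|---|---|
| 0.3 | 0.7 × 1.271 = 0.89 SD | about 100% | 0.7 × 0.798 = 0.56 SD | about 91% |
| 0.5 | 0.5 × 1.271 = 0.64 SD | about 99% | 0.5 × 0.798 = 0.40 SD | about 77% |
| 0.7 | 0.3 × 1.271 = 0.38 SD | about 90% | 0.3 × 0.798 = 0.24 SD | about 51% |
| 0.9 | 0.1 × 1.271 = 0.13 SD | about 43% | 0.1 × 0.798 = 0.08 SD | about 20% |

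**2. Windows overlap only in part.** Daily volumes were simulated without a treatment effect. Assumptions: true slope mean 2 and SD 1 units/day, daily error SD 5 to 10 with day-to-day correlation 0.5, lowest 30% enrolled, 'before' = last 10 days, 'after' = next 14 days.

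| Lack of progress judged on | Spurious gain in rate (units/day) |
|---|---|
| The same 10 days as 'before' | 0.58 to 1.6 |
| The full 14 days | 0.28 to 0.92 |
| The full 30 days | 0.03 to 0.11 |

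In the 30-day case the favourable false-positive rate is only about 4% to 6%.

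**3. 'Before' rate from days not used for selection.** With q = 0.3, r = 0.5 and equal correlation between windows, the gain falls from 0.5 × (0.3477 / 0.3) = 0.58 SD to 0.00 SD.

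**4. The same move applied to volume.** Under the assumptions of step 2, with enrolment on the last 10 days and a 10-day treatment epoch, the change in mean daily volume without any effect is 10.6 units (error SD 5) or 13.1 units (error SD 10). Much of this is natural improvement. Taking the volume baseline 10 days earlier raises it to 21.3 or 26.2 units. The added 10.7 or 13.1 units are ten more days of improvement, at about 1.1 or 1.3 units/day. An earlier baseline helps the rate and harms the volume comparison.

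**The case against.** The strongest reply is that the overlap is inferred. The plan does not say that 'before' is the stalled period, and the no-progress condition appears in E.1 but not in the numbered inclusion criteria, which speak only of poor oral feeding after 30 or 14 days. If clinicians judge a preterm infant over the whole month, step 2 shows that little bias remains. This stands, and it limits the claim to a conditional one. It does not dispose of it: E.1 makes lack of progress a condition of entry, the 14-day criterion leaves a material bias, and 7-10 day epochs make the days just before treatment an obvious choice for 'before'. The two statements of eligibility should also be reconciled.

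A second reply is that this is a pilot. The end of section B puts the feeding hypotheses after safety and feasibility, and Limitations concedes the comparison lost without sham. That is fair, and the safety and feasibility hypothesis is untouched. But Specific Aim 1 still lists volume change as a primary outcome, and Limitations mentions neither regression to the mean nor maturation.

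A reader might infer that regression to the mean alone guarantees a gain, or that the trial will probably report a false benefit. The documents do not support that: it needs coinciding windows and a moderate correlation, and neither is stated. Nor does anything in the plan say that this effect estimate will be used to size the later trial.

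**Conclusion.** The concern holds in conditional form. The plan selects on lack of progress, compares the rate of gain before and after treatment without a concurrent untreated group, and does not keep the two sets of days apart. Followed as written, it can show a favourable rate change with no taVNS effect.

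The direction follows from the design wherever the windows overlap. The size does not, because it depends on the enrolled share, the correlation and the judging window, all of which are assumed. The range runs from 0.89 SD down to values near zero, and no point in it can be called the likely one. The once- versus twice-daily comparison need not be biased if both groups enter by the same rule. No separate regression-to-the-mean figure was derived for the volume outcome, where maturation also contributes.

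**What to change.** In Data Analysis:

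1. Record for each infant the chart dates on which lack of progress was judged.
2. For the rate comparison only, take the 'before' rate from charted oral-feeding days outside those dates, where such days exist. Do not move the volume baseline earlier, because the improvement over 3-6 weeks described in Specific Aims would add to the apparent volume gain.
3. Where no separate days exist, and for before/during volume change in all infants, report the change as descriptive and not as evidence of a taVNS effect. State regression to the mean and maturation in Limitations.

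The cost is some wording and the extraction of volumes already charted. The downsides are a less precise 'before' rate, especially in term infants who may have only 14 days of oral feeding, and a weaker efficacy statement. If lack of progress is judged over the whole 30 or 14 days, few separate days may remain and item 3 carries the fix. An untreated chart cohort meeting the same entry rule, whatever its later G-tube outcome, would be a useful optional reference, but it is extra work and the fix does not depend on it.
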